6.3. Treatment protocol differences between the two arms

The FP and Dolphin CPAP machines have the following features in common:

- Simple dial setting of desired FiO_2
- Simple dial setting of desired blended gas flow rate; and
- Simple connector to the end of the expiratory tube which submerges into the PEEP bottle, to create distending pressure which varies with the depth of insertion but, as discussed immediately below, the FP and Dolphin machines are operate differently in important ways.

While these features are designed to achieve the same ends, there are two major differences that need to be checked and corrected for:

1. **PEEP:** The FP CPAP machine is designed to be used with a standard FP tube set and interface; as a result, the setting at the PEEP bottle is designed to give the desired PEEP at the end of the interface on the assumption that the standard FP circuit is used. If the 'CPAP probe' above the lid of the PEEP bottle is set to a number (the available range is 3-10), this achieves a PEEP approximately equivalent to that number at the end of the patient interface, at a flow rate of 4 L/min. With higher flow rates, the PEEP increases by approximately 0.11-0.14 cm H_2O per additional 1 L/min (i.e., at a flow of rate of 9 L/min, the PEEP at the end of the interface will be approximately 0.6 cm H_2O higher than at 4 L/min). If non-FP interfaces are used, the PEEP at the end of the interface may be different, to that shown on the FP circuit.

The Dolphin CPAP, by contrast, is designed to be used with numerous interfaces, and thus the PEEP setting is set at the actual depth of insertion of the expiratory probe in water. Setting the depth to 6cm H_2O , for example, does not indicate that 6 cm H_2O is being achieved at the end of the interface.

The Ramaiah CPAP treatment protocols are based on the FP settings, so laboratory assessment will be made of the PEEP settings required on the Dolphin CPAP to achieve the same PEEP at the end of the interface. After adjustment, the protocols will be identical in relation to PEEP delivered at the end of the interface.

2. **FiO_2 :** As FiO_2 is a primary outcome, the FiO_2 of all machines will be independently verified using the AAI model PSR-11-917-MH oxygen analyser across the full range of deliverable FiO_2 – see relevant dot point of Section 4.5. If there are calibration differences, these will be taken into account in analysis of this outcome.

As FiO_2 is also key to determining the need for other crucial interventions, differences (if found) will also be taken into account in setting Dolphin-specific treatment protocols, most importantly: oxygen requirement for surfactant ($> 40\% \text{FiO}_2$ to maintain SpO_2 of 90-95% for ≥ 30 minutes); and for intubation and mechanical ventilation ($\text{FiO}_2 \geq 60\%$ to maintain SpO_2 of 90-95% for ≥ 1 hour). As the FP CPAP is the basis of current Ramaiah protocols, we will determine the FiO_2 at the patient interface when the FP CPAP reads 40% and 60%, and ensure that the protocol for the Dolphin CPAP uses thresholds that are delivering the same FiO_2 as measured at the patient interface.

Other differences to the FP and Dolphin CPAP machines will not be calibrated, as they are intrinsic to the machines and thus relate directly to the treatment comparison.

Annex A: Data to be collected on all eligible infants

A limited number of pieces of information will be collected on all eligible infants, regardless of whether they are ultimately randomised.

This information will be used to explore the limits of generalizability of the study results, by showing how babies who were excluded, who were missed for some reason or whose guardians declined to participate in the trial, differ from the babies that were ultimately randomised. The form will indicate whether babies were:

- Excluded (no identifier);
- Missed (eligible, but consent not sought for some documented reason – no identifier);
- Declined consent (no identifier); or
- Randomised (these babies will have a unique identifier, enabling linkage to other infant information);

The information to be collected includes:

1. Specification of all three inclusion criteria. If answer to the questions is 'Yes' the form must be completed.
2. Babies not randomised, by reason (specifically, as indicated above: i) meets one or more exclusion criterion; ii) failed to seek consent; iii) consent sought but declined)
3. IF consented & randomised, record randomisation number to permit linkage; if not randomised create dummy ID number for administrative purposes in the PTNA system.
4. Maternal information:
 - a. Age (completed years)
 - b. Previous preterm birth (Y/N)
 - c. Previous perinatal death (Y/N)
 - d. Presenting antenatal problem (Unknown/PPROM/PTL/PIH/APH/IUGR/Fetal distress/Other/None/NS; If 'Other', describe)
 - e. Onset of labour (Spontaneous/Induced/No labour)
 - f. Hours from rupture of membranes to birth
 - g. Anaesthetic (None / Spinal or epidural / General / NS)
 - h. Chorioamnionitis as reason for delivery (Y/N)
 - i. Corticosteroids (Unknown/None/<24 hrs/Complete/> 7 days)
 - j. Delivery (NVD/Forceps/Vacuum/Vaginal Breech (forceps)/Vaginal Breech (no forceps) / CS/NS)
 - k. Meconium (Y/N)
 - l. Plurality (Singleton/Multiple/NS; if 'multiple', number and birth order of this infant)
5. Newborn information:
 - a. Month and year of birth
 - b. Gestation (weeks _____; days _____)
 - c. Birthweight (g)
 - d. Sex (M/F/Ambiguous/NS)
 - e. Apgar1
 - f. Apgar5
 - g. Resuscitation [highest] (None/Minimal/CPAP/Bag & Mask or T-piece/Intubation/ECM/ NS)
 - h. Indication for respiratory support (Clinical signs/Respiratory acidosis [gas]/O₂ requirement/ Apnoea/Other/NS; If 'Other' describe)

---- ENDS ----

Annex B: Data which will be collected on all randomised infants

Detailed information will be collected on a set of related forms for all randomised infants. The forms to be used includes:

1. Listing of randomised infants (one register-style form)
 - a. Randomisation number [Primary ID]
 - b. Infant's MRN [Secondary ID]
 - c. Infant's name
 - d. Mother's MRN
 - e. Mother's name
 - f. Parent phone number
 - g. Parent address
2. Adverse Event form (one per discrete AE)
 - a. Randomisation number [Primary ID]
 - b. Infant's MRN [Secondary ID]
 - c. Type of AE (Nares/Septum/Pneumothorax/IVH/ICH/PVL/ $\text{FiO}_2 \geq 60\%$ /Intubated & MV/Death/Other; If 'Other' describe; if IVH, give grading; must report separately even if the two are related, such as $[\text{FiO}_2 \geq 60\%]$ AND [intubated & MV] AND [Death])
 - d. Date and time AE diagnosed
 - e. Severity (Mild / Moderate / Severe / Life-Threatening / Death)
 - f. Outcome (Resolved – No sequelae / Resolved - Sequelae / Not resolved / Death)
 - g. Link to CPAP therapy (Definite/Likely/Possible/Unlikely/Unrelated/Unclear)
 - h. Respiratory therapy at time of event (None/Dolphin CPAP/FP CPAP/Passive/MV/Other/Unknown; if other, describe)
 - i. Text field for details, including treatment
3. General form (one per baby)
 - a. Dates and Times
 - Birth
 - Admission
 - Randomisation (allowing calculation of hours at randomisation, by subtracting date and time of birth)
 - Commencement of CPAP (allowing calculation of hours at age of CPAP commencement, by subtracting date and time of birth)
 - b. Selected information prior to treatment commencement
 - Weight at admission (g)
 - Method of respiratory support prior to randomisation, with details (the usual Ramaiah practice is to provide hood oxygen with a flow rate of 5 L/min)
 - Any unexpected delay between eligibility and randomisation? (Y/N; if Yes, describe)
 - Any unexpected delay between randomisation and treatment commencement? (Y/N; if Yes, describe)
 - c. Setting at treatment commencement
 - Prong size
 - Flow rate
 - PEEP
 - d. Primary and secondary endpoints, as measured at baseline (just prior to CPAP commencement) and 6, 12, 24, 48 and 72 hours:
 - FiO_2 ,
 - SpO_2 ;

- Respiratory rate;
- Arterial blood gases: pH, PaO₂, and PaCO₂; and
- Date and times of each reading.

e. Adverse events:

- Total number of discrete events (one AE form per discrete event);

f. Respiratory treatment details

- Surfactant? (Y/N; if Yes, number of doses, and date and time of first dose; FiO₂ at time surfactant ordered, and chest X-Ray diagnosis prior to surfactant)
- Number of apnoeic episodes during stay (0/1-4/5-9/≥ 10), as per existing Ramaiah protocol defining an apnoeic episode
- Any treatment for apnoea (No / Aminophylline / Theophylline / Caffeine / Other; if 'Other', describe);
- Date and time CPAP first ceased for 1 or more hours
- Any further CPAP provided and, if so, duration
- Hours of passive oxygen (low flow cannulae, mask or head box/hood)
- Hours of mechanical ventilation

g. Selected other treatments and diagnoses

- Treated with antibiotics (Y/N; if Yes, which antibiotics)
- Any positive blood cultures? (Y/N; If Yes, identify sample site and organism)
- Any congenital anomalies (Y/N; if Yes, describe)

h. Feeding

- Number of days of IV fluids
- Date on which infant first achieved 24 hours without IV fluids or naso- or oro-gastric feeds
- Full breastfeeding at hospital discharge (N/Y)
- Last weight prior to discharge (g), and date of this weight

i. Discharge

- First NICU discharge
- Duration of all other NICU admissions before hospital discharge
- Hospital discharge
- Final diagnosis of the early respiratory distress (RDS/TTN/Congenital pneumonia /Meconium aspiration/pneumothorax or air leak syndrome/Other/NS)
- Outcome at hospital discharge (Home/Transfer/Death/Abscond/Other)
 - If infant transferred, reason for transfer, place transferred to, and infant condition at time (Well / Uncertain / Moribund)
 - If Abscond, infant condition at time (Well / Uncertain / Moribund)
 - If Other, describe

---- ENDS ----

REFERENCES

1. Liu, L., et al., *Global, regional, and national causes of child mortality: an updated systematic analysis for 2010 with time trends since 2000*. The Lancet, 2012. **379**(9832): p. 2151-2161.
2. Lawn, J.E., et al., *Newborn survival: a multi-country analysis of a decade of change*. Health Policy & Planning, 2012. **27(suppl_3) Supplement**(3): p. iii6-iii28.
3. Baker, C.D. and C.M. Alvira, *Disrupted lung development and bronchopulmonary dysplasia: opportunities for lung repair and regeneration*. Curr Opin Pediatr, 2014. **26**(3): p. 306-14.
4. Joshi, S. and S. Kotecha, *Lung growth and development*. Early Human Development, 2007. **83**(12): p. 789-94.
5. Roberts, W.E. and J.C. Morrison, *Pharmacologic induction of fetal lung maturity*. Clinical Obstetrics & Gynecology, 1991. **34**(2): p. 319-27.

Statistical Analysis Plan

“Randomised trial comparing CPAP machines with reusable vs disposable circuits”

Introduction

1. This document sets out the statistical analysis plan for a randomised trial conducted at Ramaiah Medical College hospital, Bangalore, Karnataka, India, between June 2017 and July 2018 (inclusive). At each point, the plan sets out the text in the original plan and highlights any variations from that plan, as updated on 31 August 2019.
2. **Limitations:** There were two important limitations to the study analysis as envisaged in the protocol:
 - a. The achieved sample size was n=51. This compares to the 80 randomised infants planned for as a feasible target in the setting, despite a 5-month extension to recruitment. The planned sample size was only capable of estimating a major difference (a difference of 0.70 standard deviations between the means) in the primary outcome. The achieved sample size therefore substantially reduces the study power.
 - b. Many of the outcomes, including the primary outcome, were predicated on the assumption that staff would be targeting oxygen saturations of 90-95%, as measured through pulse oximetry (SpO_2); it transpired that this was rarely the case. SpO_2 within the 90-95% target range was achieved in 54 of 224 readings (24.1%) overall, by reading:
 - 14 of 51 (27.5%) of readings at baseline;
 - 9 of 50 (18.0%) of readings at 6 hours;
 - 9 of 49 (18.4%) of readings at 12 hours;
 - 15 of 41 (36.6%) of readings at 24 hours;
 - 4 of 24 (16.7%) of readings at 48 hours; and
 - 3 of 9 (33.3%) of readings at 72 hours.

Exclusion of other outcomes SpO_2 was outside the target readings would have markedly reduced the sample size available, so analysis was continued as planned, including all records, with a note that the analysis may be contaminated. In the case of the primary outcome, for example, the analysis interprets the amount of oxygen required as being reflective of that needed to achieve targeted saturations; when the SpO_2 is above the target range, it is difficult to ascribe meaning to the oxygen level that was provided.

Primary outcome

3. **Descriptive analysis as specified in the protocol:**

Primary and selected secondary outcomes - descriptive: The raw values of the primary outcome (FiO_2) and five secondary outcomes (SpO_2 , respiratory rate, pH, PaO_2 , $PaCO_2$) will be graphed to allow visual comparison of differences at baseline and over time. [Protocol, para 5.2]

4. **Descriptive analysis as revised:** No change.

5. **Planned analysis as described in the protocol:**

Primary outcome: With longitudinal measurement, the interpretation of later results can be impacted by differential losses before 72 hours (death or intubation and ventilation). Analysis will therefore commence with a Kaplan-Meier curve comparing ‘loss’ (death or intubation and ventilation), and an associated Cox regression model to compare the rate of loss in the

Statistical Analysis Plan

"Randomised trial comparing CPAP machines with reusable vs disposable circuits"

[figure not shown]
two treatment arms. The results of this survival analysis will provide the context within which the longitudinal results will be interpreted. If there are differential losses over time, the least affected time point will be 6 hours after treatment commencement, and this time point will be promoted to being the primary outcome. If losses over time are not differential, the planned analysis is described below.

The preferred omnibus analysis is a longitudinal mixed effects model (using PROC MIXED in SAS 9.4), controlling for baseline through a random 'intercept', in line with international recommendations for controls on baseline.^[30] Individual analyses at each time point (6, 12, 24, 48, and 72 hours) will be by multiple regression, again adjusting for baseline as a covariate.^[30] If multiple regression model requirements for normality and homoscedasticity are not met, analysis will be by t-test which is known to be robust to violations of the normality assumption, and will be based on the change in variable from baseline value, providing some control for different baselines, but without the additional control offered by multivariate analysis.

Where performed, multivariate analysis will control for stratification; if univariate analysis is used, separate stratum-specific sub-analysis will be undertaken, and a stratified t-test will be performed. Additional covariates will be adjusted for in multivariate analysis, if the baseline comparison shows substantial group difference in significant prognostic factors (e.g., onset of labour is associated with the stimulation of surfactant production, so analysis will control for mode of delivery if there is a clinically relevant mal-distribution). [Protocol, para 5.2]

6. Revisions to planned analysis:

- As noted above (para 2b), all data analysed, not just data where SpO₂ was 90-95%
- Kaplan-Meier curve produced to assess treatment failure in the first 72 hours, with difference assessed by log-rank test. Three Dolphin and one Fisher-Paykel failure in first 72 hours; not statistically different by log-rank test, $p=0.30$. Two infants ceased CPAP and were discharged <72 hours (one left against medical advice, the other discharged home), and were excluded from the denominators from the point of discharge. No control for stratification in analysis, as no failures in the older gestational group.

Statistical Analysis Plan

“Randomised trial comparing CPAP machines with reusable vs disposable circuits”

- c. While the difference between groups was not statistically significant in survival analysis, change at in FiO₂ from baseline to 6 hours was preferred as the primary endpoint, given the small sample size. As the distribution was strongly peaked, a non-distributional test (Wilcoxon) was preferred, controlling for stratification (van Elteren's extension).

Secondary outcomes

7. Descriptive analysis as specified in the protocol:

Primary and selected secondary outcomes - descriptive: The raw values of the primary outcome (FiO₂) and five secondary outcomes (SpO₂, respiratory rate, pH, PaO₂, PaCO₂) will be graphed to allow visual comparison of differences at baseline and over time. [Protocol, para 5.2]

8. Descriptive analysis as revised: No change.

9. Analyses as specified in the protocol:

Secondary outcomes: Five of the secondary outcomes (SpO₂, respiratory rate, pH, PaO₂, PaCO₂) will be analysed using the same procedures as for the primary outcome. It is anticipated that the three arterial blood gases (pH, PaO₂, PaCO₂) will not be performed on all infants, particularly infants that recover rapidly; if so, this analysis will be restricted to change from baseline at the 6-hour reading.

Duration of CPAP (hours), for those not failing CPAP treatment, is the only continuous secondary outcome this is expected to be non-normally distributed and will therefore be assessed using Wilcoxon's rank sum test, with stratum-specific contributions aggregated using van Elteren's extension to the Wilcoxon test.^[31]

The remaining secondary outcomes are dichotomous and will be tabulated and compared using stratum-specific relative risks (RRs); the homogeneity of stratum-specific RRs will be assessed using Cochran's Q and the I² tests^[32]. [Protocol, para 5.2]

10. Revisions to planned analysis:

- a. As with the primary endpoint, change from baseline at the 6-hour reading was adopted as the preferred analysis for SpO₂ (Secondary outcome #2), respiratory rate (Secondary outcome #3), pH, PaO₂, PaCO₂ (all reported as part of Secondary outcome #4) and duration of CPAP (Secondary outcome #8). Due to concerns about non-normality, van Elteren's extension to the Wilcoxon test was used to assess statistical significance, while controlling for stratification by gestational age group. No testing was performed for Secondary outcome #4 (pH, PaO₂, PaCO₂) as there were only five infants who had readings at both baseline and six hours of age.
- b. Dichotomous secondary outcomes were compared using the Cochran-Mantel-Haenszel test, with assessment for homogeneity using the Breslow-Day test. The exceptions to this were:
 - Where there were no events in one stratum (i.e., CPAP failure [Secondary outcome #5], Serious Adverse Event [Secondary outcome #9], Intubation and mechanical ventilation [Secondary outcome #15] and Death [Secondary outcome #17]), Fisher's Exact test was used on the full data; and
 - Where there were no events in either stratum (Damage to the nasal septum [Secondary outcome #10], Damage to the nares [Secondary outcome #11], Pneumothorax

Statistical Analysis Plan

“Randomised trial comparing CPAP machines with reusable vs disposable circuits”

diagnosed by X-Ray [Secondary outcome #12], Intra-ventricular haemorrhage (IVH), intra-cranial haemorrhage (ICH), or periventricular leukomalacia (PVL) as diagnosed by cranial ultrasound scan [Secondary outcome #13], $\text{FiO}_2 \geq 60\%$ to maintain SpO_2 at 90-95% for one hour or more, during CPAP treatment [Secondary outcome #14] and, for infants born at 28+0 to 33+6 weeks' gestation, oxygen dependent at 36 weeks' gestation [Secondary outcome #16]), no statistical test was performed.

Other issues

11. **Multiple comparisons:** The principal control for multiple comparisons was the designation of a single primary endpoint.

As an exploratory study, with a small planned sample size determined by time available for recruitment rather than a definitive assessment of a pre-determined clinically significant difference in endpoints, it was decided that no adjustments would be made for multiple comparisons of secondary endpoints, many of which were sentinel events. Rather any statistically significant results would be assessed within the context of the primary endpoint result, and with full acknowledgement of the risks of multiple comparisons.

ENDS

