Randomised trial comparing CPAP machines with reusable vs disposable circuits

STEERING COMMITTEE

Primary Investigator:

[name] [name], MS Ramaiah Medical College

Co-investigators:

[name] M, MS Ramaiah Medical College

[name] MV, MS Ramaiah Medical College

Other Guidance:

The Wellcome Trust Research Steering Group provided assistance and guidance with protocol design.

Members providing technical input included:

[name], Neonatologist, in the role of Consultant to the Wellcome Trust

[name], Consultant to MTTS

PARTICIPATING SITES

M.S. Ramaiah Medical College, Bangalore, Karnataka, India.

TRIAL CONTACT

[name] [name]

MS Ramaiah Medical College

Email: [contact]

[contact]

INSTITUTIONAL ETHICS COMMITTEE

[name] (Chairman)

Ethics Committee

M S Ramaiah Medical College and Hospitals

[name]

[name]

Email: [contact]; [contact]

[contact]

TRIAL SUMMARY

1. Aim & Hypothesis:

The study aims to assess the basic functionality of a newly designed CPAP machine with reusable circuits to existing machines with disposable circuits, for treatment of newborn infants diagnosed with respiratory distress syndrome. The assessment will compare a comprehensive list of physiological parameters over the first 72 hours of treatment, and will also monitor rates of side effects and adverse events. The null hypothesis is that infants treated on the two categories of machine (reusable vs disposable) will not differ in relation to key physiological parameters by more than 0.63 standard deviations.

2. **Background:**

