4.7. Trial funding

Funding is being provided through Thrive Networks, which is in receipt of funding from the Wellcome Trust under the R&D for Affordable Healthcare in India scheme. The purpose of this project, entitled “Continuous Positive Airway Pressure (CPAP) machine to promote rational oxygen use for neonates and to reduce the incidence of retinopathy of prematurity (ROP)” is to develop and commercialise a low-cost CPAP machine for the Indian marketplace.

5. Sample size and statistical analysis:

5.1. *Sample size calculation*

Sample size calculations are based on the primary outcomes. All the outcomes are selected to be continuously distributed. A sample size of 40 infants per group has been selected as something that is achievable at the anticipated recruitment rate at Ramaiah Hospital in the time available (10 months, including 8 months for recruitment at 10 randomised infants/month). The trial will cease when 40 infants have been randomised to each arm (i.e., at this point the other arm must have 40 or more randomised infants). With this sample size, a difference of 0.63 standard deviations is detectable, with 80% power ($1-\beta$) and a 5% false-positive rate (α). We lack data, within the study population, on the anticipated outcomes in the primary and secondary endpoints.

Feasibility: An assessment of eligible infants meeting the inclusion criteria (and none of the exclusion criteria) in February and March 2016 (two complete months) identified:

- 24 inborn neonates eligible for randomisation (i.e., 12/month); and
- 11 outborn neonates admitted to Ramaiah <6 hours of age (i.e., 5.5 /month).

This give a total of 17.5 eligible infants per month. Previous experience at Ramaiah is reported to be a 70% recruitment rate which, if maintained in the current study, would yield an average of 12.2 randomised infants/month. This is above the required randomisation rate of 10 infants per month, and suggests that the project would be feasible with a 60% recruitment rate.

5.2. *Statistical analysis*

Primary and selected secondary outcomes - descriptive: The raw values of the primary outcome (FiO_2) and five secondary outcomes (SpO_2 , respiratory rate, pH, PaO_2 , PaCO_2) will be graphed to allow visual comparison of differences at baseline and over time.

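### SAP 2a gives 0.70 SD as the difference detectable with the planned 80 infants; the protocol gives 0.63 SD for the same sample, and only 0.63 follows from its stated power and alpha

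*SAP*

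**What the plan says.** Protocol section 5.1 starts from feasibility: "A sample size of 40 infants per group has been selected as something that is achievable" at the expected recruitment rate. It then gives what that number can detect: "With this sample size, a difference of 0.63 standard deviations is detectable, with 80% power" and a 5% false-positive rate, without saying whether the test is one- or two-sided. The same effect size appears in the hypothesis in protocol section 1, where infants on the two machine types "will not differ in relation to key physiological parameters by more than 0.63 standard deviations".

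SAP paragraph 2a compares the 51 infants achieved with the 80 planned and says of the plan: "The planned sample size was only capable of estimating a major difference (a difference of 0.70 standard deviations between the means". It attaches no power, alpha or attrition to this figure. It concludes: "The achieved sample size therefore substantially reduces the study power". SAP paragraph 1 describes how the document treats departures from the protocol: "At each point, the plan sets out the text in the original plan and highlights any variations from that plan". The change from 0.63 to 0.70 is not mentioned.

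**The concern.** One planned sample has two detectable differences. A reader of the SAP cannot tell whether 0.70 is a slip or a recalculation on inputs that were not reported.

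What is at stake is limited but real. The figure is the only effect size in the SAP's account of power, and it is the starting point for the statement that the shortfall in recruitment cost power. If the starting point is too large, the planned trial looks less sensitive than it was, and the loss from 80 to 51 infants looks smaller than it was.

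**Working it through.** **Inputs.** 40 per arm, 80% power and alpha 5% (protocol 5.1). The effect is in SD units, so SD = 1. Sidedness is not stated; two-sided is assumed first and one-sided is tried as well.

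**1. The protocol's figure.** The normal approximation for the detectable difference is

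d = (z for alpha + z for power) × √(2/n) = (1.960 + 0.842) × √(2/40) = 2.802 × 0.2236 = 0.626 SD.

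The exact t-test calculation (noncentral t, 78 degrees of freedom) gives 0.634 SD. Both round to 0.63. Power at exactly 0.63 SD is 80.4% (normal) or 79.5% (t). The protocol's figure is reproduced.

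**2. The SAP's figure on the same inputs.**
- Power at d = 0.70 with 40 per arm: the standardised shift is 0.70 / √(2/40) = 3.130, and 3.130 − 1.960 = 1.170, which gives 87.9% (normal). The noncentral t gives 87.1%.
- Number per arm for d = 0.70 at 80% power: 2 × 2.802² / 0.70² = 32.0 by the normal approximation, and about 33 by the t-test.

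So 0.70 is not the 80%-power figure for 40 per arm.

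**3. Can another reading give 0.70?** Detectable differences by t-test, two-sided 5% and 80% power unless noted:

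| Reading | Detectable difference (SD) | Stated in the documents? |
|---|---|---|
| 40 per arm, two-sided 5% | 0.634 | Yes, apart from sidedness |
| 40 per arm, one-sided 5% | 0.56 | Sidedness not stated |
| 40 per arm, 90% power | 0.734 | No |
| 40 per arm, two-sided alpha 2.5% | 0.701 | No |
| 33 per arm analysed (1 − 33/40 = about 17% loss) | 0.700 | No |
| 40 per arm, Wilcoxon, normal data | 0.65 | Not the planned test |
| 40 per arm, Wilcoxon, efficiency 0.864 | 0.68 | Not the planned test |
| 51 infants, assumed 25/26 | 0.80 | Achieved sample, not planned |

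Only an unstated attrition allowance, an unstated alpha or an unstated power of about 87% gives 0.70. The figure does not belong to the achieved sample either.

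**4. What the baseline does to the statement on lost power.** The split of the 51 infants is not given, so a near-equal split and an unadjusted t-test are assumed.
- 25/26: detectable difference 0.80 SD; power for 0.63 SD is 60%.
- 22/29: 0.81 SD and 59%.
- 25/25: 0.81 SD and 59%. This applies if FiO₂ at 6 hours has the same count as SpO₂, for which SAP 2b reports "9 of 50 (18.0%) of readings at 6 hours".

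On the protocol's basis the detectable difference goes from 0.63 to about 0.80 SD, a change of 0.17. Measured from 0.70 it appears as 0.10.

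SAP 6c later changed the test: "As the distribution was strongly peaked, a non-distributional test (Wilcoxon) was preferred". For a Wilcoxon test the value depends on the shape of the distribution. At 25/26 and under normality (efficiency 0.955) it is about 0.82 SD.

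**The case against.** The strongest reply is that the number does no work. It stands in a limitations paragraph of a SAP updated on 31 August 2019, after the trial had run from June 2017 to July 2018. It affects no test, and the protocol's 0.63 remains the basis of the sample size. Protocol 5.1 and SAP paragraph 11 both say that recruitment time set the sample size, and the SAP already says in words that only a major difference was within reach and that power fell. A reader would draw much the same conclusion from either figure. This stands, and it is why the point is minor.

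A second reply is that no stated calculation fails in SAP 2a, because it gives no inputs; 0.70 is correct for about 87% power or for about 33 analysed per arm. That is also fair. What is shown is a contradiction between the documents, and that 0.70 does not follow from the protocol's inputs; its origin is unknown. The fix therefore allows the sponsor to justify the figure instead of changing it.

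Two smaller replies concern wording. The protocol does not state sidedness, but the one-sided reading gives 0.56 SD and moves further from 0.70. The promise to highlight variations is carried out mainly in the paired items from paragraph 3 onwards, so the missing flag in paragraph 2 adds little to the mismatch itself.

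**Conclusion.** The concern holds. For the planned 40 per arm, the figure consistent with the protocol is 0.63 SD (0.634 by t-test, 0.626 by normal approximation, both two-sided). The SAP's 0.70 SD overstates the detectable difference by about 0.07 SD and corresponds to 87.1% power, not 80%. The result rests on one assumption, that the 5% is two-sided, and the one-sided reading does not rescue 0.70.

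The consequence is confined to reporting: the plan is described as less sensitive than it was, and the loss from under-recruitment looks smaller than it was. No analysis or result changes. The figures for 51 infants are context only and rest on the assumed split and test.

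**What to change.** In SAP 2a, replace 0.70 with 0.63 SD and state the inputs: 40 per arm, 80% power, two-sided 5%. If 0.70 was intended, state the power, alpha or attrition behind it and list it as a variation from the protocol.

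Optionally, add one sentence next to the remark on reduced power, with its assumptions: with 51 infants, a near-equal split and an unadjusted t-test, the detectable difference is about 0.80 SD and power for 0.63 SD is about 60%; for the van Elteren Wilcoxon test the value depends on the distribution. The sponsor should compute this from the actual split and the actual number of infants with FiO₂ at both baseline and 6 hours.

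The cost is one number in one sentence, with no re-analysis. The correction makes the planned sensitivity look slightly better; only the optional sentence is less favourable to the trial.
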